CLINICAL PROTOCOL

The CHECK Trial: A Comparison of Headache Treatment in the Emergency Department: Prochlorperazine versus Ketamine

INTRODUCTION

In the emergency department (ED), one of the most common chief complaints is headache [1]. A number of prior studies have demonstrated the efficacy of a variety of medications for migraines and other benign headaches [2]. Some of the options for treating these types of headaches include dopamine antagonists, opioids, non-steroid anti-inflammatory drugs (NSAIDs), triptans, anti-epileptics, and ergot derivatives [2]. Amongst the available options, dopamine antagonists appear to be the most effective, with multiple studies demonstrating their superiority over opioids [3], NSAIDs [4], triptans [5], and anti-epileptics [6]. The dopamine antagonist that we use most frequently, and the one that has the most evidence to support its use for benign headaches, is prochlorperazine [5,6,7,8,9,10]. Although some data suggest that droperidol may be even more effective than prochlorperazine [11], the current national shortage limits its use.

Despite the general effectiveness of dopamine antagonists and the variety of options for benign headache treatment, many patients who present to the ED still have headaches 24 hours after treatment. In one study by Friedman, 31% of patients still had moderate to severe headaches 24 hours after discharge [12]. Often we resort to opiates in refractory headaches despite evidence to suggest that opiates increase both length of stay and bounce backs [13].

Ketamine is a NMDA receptor antagonist that has both analgesic and dissociative properties [14]. Previous studies have demonstrated the effectiveness of ketamine for post-operative pain [15,16], pain in burn patients [17], and chronic pain [18]. New studies have also shown ketamine to be useful for acute pain in the ED by both the intranasal [19] and intravenous routes [20]. To our knowledge, there are no prospective studies that evaluate the effectiveness of ketamine for the treatment of benign headaches in the ED.

We propose a double blind, randomized control study comparing ketamine to prochlorperazine for benign headaches in the ED.

METHODS

Study Design

This will be a multicenter, prospective, double-blinded, randomized controlled trial on a convenience sample of patients presenting to the ED with a chief complaint of headache.

Subjects will only be enrolled when a pharmacist who is familiar with the study protocol is available to prepare medications.

Exempt from FDA IND#

This study meets the requirements in 21CFR312.2(b)Exemptions(1) to exclude this study drug from registration for FDA IND# .

“21CFR312.2(b)Exemptions(1) The clinical investigation of a drug product that is lawfully marketed in the United States is exempt from the requirements of this part if all of the following apply:

“(i) The investigation is not intended to be reported to the FDA as a well-controlled study in support of a new indication for use nor intended to be used to support any other significant change in the labeling for the drug;

Investigators do not intend to report study data to the FDA to support label changes for Ketamine.

“(ii) If the drug that is under investigation is lawfully marketed as a prescription drug product, the investigation is not intended to support a significant change in the advertising for the product;

Investigators do not intend to provide support for changes in advertising for Ketamine.

“(iii) The investigation does not involve a route of administration or dose level or use in a patient population or other factor that significantly increases the risk (or decreases the acceptability of the risks) associated with the use of the drug product;

Investigators intend to administer Ketamine via the routine IV route at doses lower than typically ordered which will not alter the risk profile of the drug.

“(iv) The investigation is conducted in compliance with the requirements for institutional review set forth in part 56 and with the requirements for informed consent set forth in part 56; and

This investigation will be conducted with UMC IRB approval with Written Informed Consent.

“(v) The investigation is conducted in compliance with the requirements of §312.7.”

Study investigators will be compliant with 21CFR312.7 Which prohibits:

“(a) promotion of an investigational new drug..., (b) Commercial distribution of an investigational new drug..., (c) prolonging an investigation..., (d) charging for and commercialization of investigational drugs...”

Selection of Participants

Previous data have found that patients presenting to the ED with an undifferentiated headache improve with all the above-described headache medications regardless of whether or not they meet the definition of migraine, tension headache, or another primary headache disorder [6,8,10]. Therefore, this study will enroll all patients between the ages of 18 and 65 who meet all of the inclusion criteria and do not meet any of the exclusion criteria, who present to the ED with a benign headache.

Inclusion Criteria

Patients who present to the ED with complaint of a headache with the following criteria:

- Age 18 to 65 years
- Temperature < 100.4° F
- Diastolic blood pressure < 104 mm Hg,
- Normal neurologic exam and normal mental status

Exclusion Criteria

- Pregnant or breastfeeding.
- Meningeal signs are present
- Acute angle closure glaucoma is suspected.
- Head trauma within the previous two weeks
- Lumbar puncture within the previous two weeks
- Thunderclap onset of the headache
- Weight more than 150 kg or less than 40 kg.
- Known allergy to one of the study drugs.
- History of schizophrenia or bipolar disorder.
- History of intracranial hypertension.
- Is a prisoner
- Patient declined informed consent
- Non-English speaking patient.
- Attending provider excludes patient
- Patient received any pain medication prior to enrollment

Written, informed consent will be obtained from each patient. Consent will include a discussion of the risks and benefits. The risks are the side effects associated with each drug. For compazine, this includes drowsiness, blurred vision, xerostomia, congestion, nausea, akathisia, tardive dyskinesia, NMS, and blood dyscrasias. For ketamine, this includes, sialorrhea, nausea/vomiting, elevation in blood pressure or heart rate, nystagmus/diplopia, fasciculations, hallucinations, bradycardia or hypotension, arrhythmias, and respiratory depression. Personal benefits include intended reduction in headache symptoms and the satisfaction that the patient may be assisting investigators in determining a more effective headache treatment.

Interventions

After enrollment, each patient will randomized either to the standard treatment arm to receive prochlorperazine 10 mg IV along with diphenhydramine 25 mg IV, OR to the

study arm to receive ketamine 0.3 mg/kg along with ondansetron 4 mg IV. The diphenhydramine or ondansetron will be administered first, and immediately afterward the prochlorperazine or ketamine will be administered. The prochlorperazine or ketamine will be diluted in saline so that the total volume is 5 mL, and will be administered over 2 minutes. The diphenhydramine will be diluted in saline so that it is 2 mL (the same volume as the ondansetron). Both groups will also receive a 500 mL normal saline bolus after the study medications are administered. The ED pharmacist will be responsible for preparing the medications, using a double-blind protocol. He or she will record which arm the patient was randomized to. Only the pharmacist will have access to the randomization records and will not reveal the randomization until the end of the study. Emergency providers will be instructed not to administer any rescue medications for at least 30 minutes. The electronic medical record order will read “randomized study medication” (for the ketamine or prochlorperazine) and “randomized add-on medication” (for the ondansetron or diphenhydramine).

Safety

After 30 minutes, the treating provider will be permitted to administer any medication they would like for further treatment. If there is an untoward event that requires the treating provider to know which medication was administered, the pharmacist will unblind the randomization for that individual patient and the patient will not continue in the study.

Reportable Events

Anticipated side effects are those listed on the manufacturer’s package insert and are treated as routine non-urgent or non-emergent events are not reportable events.

Adverse Events are those unanticipated side effects that require interventions or anticipated side effects that do not respond to intervention.

Serious Adverse Events are those side effects that require Advanced Life Support measures to control symptoms.

AEs and SAEs will be reported to the IRB within 5 days of the event.

Methods of Measurement

Enrolled patients will fill out a brief data collection form to include age, sex, race, phone number, and baseline headache severity using a 100-mm visual analog scale (VAS). Repeat headache severity scores will be measured at 15, 30, 45, and 60 minutes. Time zero begins immediately after complete administration of the study drug. Nausea (with a 100 m VAS), vomiting, anxiety, restlessness (akathisia), heart rate, and blood pressure will also be assessed at these time intervals. The need for rescue medications will be extracted from the patient’s chart at a later time.

Trained research assistants will call the patient 24-48 hours post-discharge by phone to ask them to rate their satisfaction with the drug they received on a scale of 0-10, and to

ask if they are currently having a headache (yes or no). If the patient is admitted, the patient will be approached in the hospital by an investigator or research assistant for follow up.

Outcome Measures

The primary outcome measure will be the difference in pain scores between the prochlorperazine and ketamine groups, measured as the absolute difference between the means at 60 min. Secondly, we will measure the difference between the rates of decline in pain scores, rate of admission, nausea scores, rate of vomiting, rate of development of akathisia, rate of use of additional medications for headache, heart rate and blood pressure changes, headache resolution with telephone follow up, and patient satisfaction.

Privacy and Security

In order to protect the privacy of the research subjects and to maintain the confidentiality of data, all data will be managed only by trained research assistants or investigators and will be stored in the locked Emergency Medicine research offices and electronic data will be stored on a password protected computer in the locked Emergency Medicine research office. All research assistants and investigators are HIPAA- trained, CITI trained and credentialed by UMC IRB, and oriented to the study protocol.

Data Analysis:

A couple prior studies have used a 25-mm difference in mean VAS score reduction between groups to show a clinical benefit [6,9]. We define significant pain relief as an absolute decrease in the mean VAS score of 25 mm.

Thirty-two patients will be needed in each group to find a 25-mm difference between the group means on the VAS at 60 min, with a power of 0.80 and an alpha of 0.05. We will aim for 35 patients per group to account for about a 10% dropout rate. The groups will be compared using a *t*-test on gender, race, and age; and a chi (with Yates correction)-squared test on severity of presenting headache, to determine if they are similar. The individual VAS measurements will be compared using a repeated measures analysis of variance (ANOVA) test.

References:

- [3] Cicek M, Karcioğlu O, Parlak I, et al. Prospective, randomised, double blind,

controlled comparison of metoclopramide and pethidine in the emergency treatment of acute primary vascular and tension type headache episodes. *Emerg Med J.* 2004;21:323-326.

[7] Jones J, et al. Randomized double-blind trial of intravenous prochlorperazine for the treatment of acute headache. *JAMA.* 1989;261:1174-1176.

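### Harms are elicited selectively: akathisia is assessed on schedule, but hallucinations, visual effects, respiratory depression and drowsiness are not, so a balanced tolerability comparison is not possible

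*Combined protocol and SAP*

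**What the plan says.** The consent paragraph under Selection of Participants sets out the expected risks of each drug. For ketamine these are sialorrhea, nausea/vomiting, raised blood pressure or heart rate, nystagmus/diplopia, fasciculations, and "hallucinations, bradycardia or hypotension, arrhythmias, and respiratory depression". "For compazine, this includes drowsiness, blurred vision, xerostomia, congestion, nausea, akathisia, tardive dyskinesia, NMS, and blood dyscrasias". The Introduction also describes ketamine as having dissociative properties, so perceptual effects are anticipated.

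Methods of Measurement fixes the schedule: "Repeat headache severity scores will be measured at 15, 30, 45, and 60 minutes". Nausea is rated on a VAS, and "vomiting, anxiety, restlessness (akathisia), heart rate, and blood pressure will also be assessed at these time intervals". No perceptual, visual, respiratory or sedation item appears. The telephone call at 24 to 48 hours asks about satisfaction and current headache only.

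Under Outcome Measures, the secondary outcomes that bear on harm are contained in "nausea scores, rate of vomiting, rate of development of akathisia, rate of use of additional medications for headache, heart rate and blood pressure changes". Anxiety is collected but is not in that list.

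**The concern.** The sponsor names the effects it expects from each drug, then collects only some of them. Among symptoms listed for one drug and not the other, prochlorperazine's akathisia is assessed at four times in every patient and compared by arm. Ketamine's hallucinations and diplopia are not asked about. Respiratory depression has no measurement, and prochlorperazine's drowsiness and blurred vision are also missing.

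The Introduction says the authors know of no prospective study of ketamine for benign headache in the emergency department. Readers will therefore look to this trial for tolerability as well as pain relief. If an effect was never asked about, a low or absent count in the report carries no information, yet it would stand beside an elicited akathisia rate as though the two were alike.

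**Working it through.** The point rests on matching lists, not on a figure in the plan. The plan's sample size enters only as the denominator for harm rates: 32 evaluable and 35 enrolled per group (Data Analysis).

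**Step 1. Match each consent entry to the schedule and the outcome list.** The consent paragraph gives nine entries per drug.

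| Drug | Consent entry | Assessed at 15, 30, 45, 60 min | Secondary outcome |
|---|---|---|---|
| Ketamine | Nausea/vomiting | Yes | Yes |
| Ketamine | Raised blood pressure or heart rate | Yes | Yes |
| Ketamine | Bradycardia or hypotension | Yes, through heart rate and blood pressure | Yes |
| Ketamine | Hallucinations | No | No |
| Ketamine | Nystagmus/diplopia | No | No |
| Ketamine | Respiratory depression | No | No |
| Ketamine | Sialorrhea; fasciculations; arrhythmias (3 entries) | No specific item | No |
| Prochlorperazine | Nausea | Yes | Yes |
| Prochlorperazine | Akathisia | Yes | Yes |
| Prochlorperazine | Drowsiness | No | No |
| Prochlorperazine | Blurred vision | No | No |
| Prochlorperazine | Xerostomia; congestion; tardive dyskinesia; NMS; blood dyscrasias (5 entries) | No | No |

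Coverage is 3 of 9 for ketamine and 2 of 9 for prochlorperazine. For ketamine's perceptual, visual and respiratory effects it is 0 of 3.

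**Step 2. Look for another route.** The 24 to 48 hour call has no harms question. Under Reportable Events, an anticipated effect counts as an adverse event only if it does not respond to intervention, and as serious only if it needs Advanced Life Support. A brief hallucination that settles unaided meets neither definition. That section governs reports to the IRB and does not forbid recording such an effect, but no section provides for collecting it from every patient.

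**Step 3. Size, under assumed rates.** The documents give no event rates, so those below are assumptions.

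- Expected ketamine patients affected: 35 × 0.10 = 3.5; 35 × 0.20 = 7.
- If the effect were elicited in all patients, the chance of seeing at least one case is 1 − (1 − p)^n:

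| Assumed rate p | n = 35 | n = 32 |
|---|---|---|
| 2% | 0.507 | 0.476 |
| 5% | 0.834 | 0.806 |
| 10% | 0.975 | 0.966 |
| 20% | above 0.999 | 0.999 |

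- If elicited and none were seen, the upper end of the exact two-sided 95% interval is 1 − 0.025^(1/n): 10.0% for n = 35 and 10.9% for n = 32.
- Power to separate the arms is limited: with 35 per arm, about 0.47 for 20% against 5%, and about 0.80 for 30% against 5%.

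Elicited items would therefore give useful descriptive rates and bounds, not a powered test.

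**The case against.** A reader might infer that the harms comparison is tilted towards ketamine. The documents do not support that. Vomiting, heart rate and blood pressure are listed as risks for ketamine only, and all three are collected and compared. Restlessness is the only collected item listed for prochlorperazine alone. Nausea is listed for both. The comparator has gaps of its own, including drowsiness, the first risk named for it. A tilt appears only if akathisia is set against hallucinations and the rest is ignored, and that pairing is not in the plan.

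Three further objections have force:

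- Restlessness is assessed, but no scale or threshold is given. The akathisia outcome is itself loosely defined, so the contrast is between an item that is asked about and items that are not.
- A reader might take the rule on anticipated effects to mean that they go unrecorded. It determines what is reported to the IRB, and the documents do not say how side effects are charted.
- Asking about hallucinations at 15, 30 and 45 minutes could reveal the arm to patient or assessor before the self-rated 60-minute VAS, the primary outcome of a double-blind trial. This affects how the fix should be built.

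One can also say that this is a trial of pain relief and that the choice of secondary harms is a matter of preference. That limits the weight of the point. It does not remove it, because the plan already chooses to compare some harms by arm.

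**Conclusion.** The point holds as one of selective elicitation affecting both drugs. Followed exactly, the plan yields an akathisia rate by arm and no by-arm rate for ketamine's hallucinations, diplopia or respiratory depression, or for prochlorperazine's drowsiness and blurred vision. It cannot support a balanced statement on tolerability. The direction of any net bias is not established.

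The finding itself needs no assumption; it follows from comparing the lists. Its size depends on unknown event rates: at an assumed 10% to 20%, an expected 3.5 to 7 of 35 ketamine patients would have an effect that the form does not ask about. The 60-minute pain comparison is unaffected. This is a cheap improvement worth making, not a defect in the primary analysis.

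**What to change.** - **Checklist.** Add the same short yes/no checklist to the existing form in both arms: hallucination or a sense of unreality, double or blurred vision, and drowsiness. Ask it once, immediately after the 60-minute pain VAS is completed, with reference to the whole hour. Asked then, it cannot influence the primary outcome.
- **Respiratory rate.** Record it with the heart rate and blood pressure already taken, and state in advance how it will be summarised.
- **Outcomes.** List these items, and the anxiety assessment already collected, as secondary safety outcomes compared by arm. Present them as rates with confidence intervals.
- **Interpretation.** Describe all harm comparisons as comparisons of drug pairs, because prochlorperazine is given with diphenhydramine and ketamine with ondansetron.

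The cost is an estimated minute more of form time, some prompted reporting in both arms, and recall over one hour in place of answers at each time point. Because other medication is permitted after 30 minutes, some symptoms reported for the hour may follow rescue treatment; the akathisia assessments at 45 and 60 minutes already share that limit. The less prominent consent entries, such as sialorrhea and xerostomia, would remain unelicited, and the report should say so. Treatment, sample size and the primary analysis do not change.

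### Unblinding for an untoward event appears to end a patient's measurements, and the plan does not say how such a patient is analysed (minor).

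*Combined protocol and SAP*

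**What the plan says.** Under Interventions, an add-on drug is followed by the study drug, which "will be administered over 2 minutes". The section then adds: "Both groups will also receive a 500 mL normal saline bolus after the study medications are administered". No later study treatment is described.

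Under Safety, unblinding is reserved for an "untoward event that requires the treating provider to know which medication was administered". In that case "the pharmacist will unblind the randomization for that individual patient and the patient will not continue in the study".

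Methods of Measurement sets the schedule: "Repeat headache severity scores will be measured at 15, 30, 45, and 60 minutes". The clock is defined there too: "Time zero begins immediately after complete administration of the study drug". A telephone contact at 24-48 h asks about satisfaction and current headache. For inpatients the section provides: "If the patient is admitted, the patient will be approached in the hospital by an investigator or research assistant for follow up". Rescue medication is read from the chart afterwards.

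Outcome Measures makes the primary outcome the difference between the arm means at 60 min. Data Analysis gives 32 patients per group for a 25-mm difference, raised to 35 for about 10% dropout, and a repeated measures ANOVA for the VAS scores. It defines no analysis set, no handling of missing or partial scores, and no sensitivity analysis.

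**The concern.** The clause ties two separate things together: breaking the blind for one patient, and ending that patient's part in the study. In a trial of repeated dosing the second could mean stopping treatment. Here, after the first few minutes, little is left to stop except observation.

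The reason for leaving arises after randomisation and may be caused by the drug. The risks listed for consent under Selection of Participants differ by drug. For prochlorperazine they include drowsiness and akathisia; for ketamine they include "hallucinations, bradycardia or hypotension, arrhythmias, and respiratory depression". Exits can therefore differ by arm.

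Three consequences follow:

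- A patient unblinded before 60 min contributes nothing to the primary comparison.
- A conventional complete-case repeated measures ANOVA would also discard that patient's earlier scores.
- Vomiting, akathisia, heart rate and blood pressure are assessed at the same times, so those outcomes lose follow-up in patients who had an untoward event. Some possible triggers, such as hallucinations or respiratory depression, match no listed outcome, and no count of unblindings by arm is planned.

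At stake is whether the groups analysed are still the groups randomised.

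**Working it through.** **1. What the clause can stop.** Before the push and bolus are complete, leaving the study could affect treatment. After that, the planned items still open are the scores at 15, 30, 45 and 60 min and the 24-48 h contact. Unblinding after 60 min leaves the primary score intact. Chart data on admission and rescue use may remain available, though the plan does not say they are collected for a patient who has left.

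**2. The plan's own figures.** Inflating 32 for 10% dropout gives 32/0.9 = 35.6, or 36. The plan's 35 is within rounding of *about* 10%, since 3/35 = 8.6%. The base figure of 32 cannot be rebuilt directly because no SD is stated. Solving backwards with 32 per group, 25 mm, power 0.80 and alpha 0.05 (two-sided assumed, noncentral t) gives SD = 35.14 mm. Check: 25/(35.14 × √(2/32)) = 25/8.785 = 2.85, the noncentrality that gives 80% power. If the test were one-sided, the SD would be 39.6 to 40.2 mm.

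**3. Loss of numbers alone.** With the SD rounded to 35 mm and 35 per group, power is 83.8% with nobody lost, 82.0% with 3 lost from one arm, and 80.3% with 3 lost from each. Power is not the issue.

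**4. Shift in an arm mean.** If k of 35 patients are lost and their 60-min scores would have differed from the rest of the arm by g mm, the observed mean is off by k × g/35, in either direction. Both k and g are assumed, and all losses are placed in one arm. SE of the difference = 35.14 × √(1/35 + 1/(35 − k)). The last column is the two-sided rejection rate with no true difference (normal approximation).

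| k | g (mm) | Shift (mm) | Share of 25 mm | SE (mm) | Rejection rate |
|---|---|---|---|---|---|
| 1 | 20 | 0.57 | 2.3% | 8.46 | 5.05% |
| 2 | 40 | 2.29 | 9.1% | 8.53 | 5.8% |
| 3 | 50 | 4.29 | 17.1% | 8.59 | 7.9% |

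For k = 2 and a true 25-mm difference, power is 82.4% with no shift, 74.7% at 25 − 2.29 mm and 88.4% at 25 + 2.29 mm (noncentral t, 66 df).

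**5. Bound without assuming g.** On a 100-mm scale, k missing scores leave the arm mean uncertain by 100k/35: 2.86, 5.71 and 8.57 mm for k = 1, 2 and 3. These are 11%, 23% and 34% of 25 mm. Neither this bound nor the shifts in step 4 depend on the SD.

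**The case against.** The strongest reply is that this may never happen. The trigger requires an event for which the provider must know the drug, and it touches the primary outcome only if it occurs before the 60-min score. No rate is given, and zero unblindings among 70 patients is plausible. That stands, and it is why the point is minor.

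The illustration is also open to challenge, fairly. It places every loss in one arm with one sign, whereas losses in both arms with gaps of the same sign would partly cancel. Gaps of 40 and 50 mm exceed the implied SD. The three-patient case spends the plan's whole dropout allowance in that arm on unblinding. The error rates are for a two-sample comparison at 60 min, not for the stated ANOVA.

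A reader might infer more than the text supports:

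- *That the protocol expressly stops the scores.* It does not name which assessments end.
- *That data already collected are thrown away.* Nothing says so; the risk comes from an unspecified ANOVA.
- *That the primary result is materially biased, or biased towards one drug.* Losing patients with poor relief flatters their arm, and losing those with good relief does the opposite. The documents give no basis for choosing, and the 7.9% figure comes from assumed inputs.
- *That the safety information is lost.* Adverse events go to the IRB within 5 days and the pharmacist records each patient's arm, so a by-arm count could be rebuilt. It is simply not planned, and side effects treated as anticipated and routine are not reportable.

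Finally, the missing analysis set and missing-score rule affect dropout from any cause. That is true, and it makes the analysis part of the remedy useful even if nobody is unblinded. The dropout allowance does not answer the point: it adds patients but does not say how those lost are analysed.

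**Conclusion.** The point holds as a minor one. On its plain reading, the Safety clause writes into the protocol a loss of outcome data that follows randomisation and may be related to treatment, and nothing in Data Analysis deals with that loss. The likely effect is small and its direction unknown. The 2.3-mm shift depends on 2 of 35 patients being lost from one arm with a 40-mm gap. The error rates further depend on an SD of about 35 mm, back-solved for a two-sided test. The bound of 2.9 mm per missing score needs only the 100-mm scale and 35 patients in the arm. The finding concerns measurement and analysis; it takes no position on when to unblind or how to manage the event.

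**What to change.** Leave the decision to unblind and the handling of the event untouched. In Safety, replace the clause that ends the patient's participation, rather than adding a sentence after it, since the two would conflict. Suggested wording:

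*Unblinding does not by itself end data collection. Planned assessments to 60 min and the 24-48 h contact continue where possible and with the patient's agreement, data already collected are kept, and the time and reason for unblinding are recorded.*

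In Data Analysis, state that:

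1. All randomised patients are analysed in their assigned arm, with a method that keeps those with incomplete scores, for example a mixed model for repeated measures with the 60-min contrast.
2. The number of unblindings and the reasons for them are reported by arm.
3. One sensitivity analysis excludes scores taken after unblinding.
4. A second varies the missing 60-min scores by arm, for example by shifts of 10 to 50 mm or values of 0 and 100 mm.

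The cost is a protocol amendment, a few sentences and one by-arm table. No patients or visits are added, because the assessments and the in-hospital follow-up are already planned. Two drawbacks remain. A few self-reported scores may come from patients who know their arm, which item 3 examines. Some scores may be unobtainable during the event, which item 4 examines. Whether consent wording must also change cannot be judged, because the consent pages are not in the text reviewed.

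### A listed side effect that is treated, responds and needs no Advanced Life Support has no clear reporting route, even if it breaks the blind

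*Combined protocol and SAP*

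**What the plan says.** The Reportable Events section has four sentences.

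- Anticipated effects: "Anticipated side effects are those listed on the manufacturer’s package insert and are treated as routine non-urgent or non-emergent events are not reportable events".
- AEs: "Adverse Events are those unanticipated side effects that require interventions or anticipated side effects that do not respond to intervention".
- SAEs: "Serious Adverse Events are those side effects that require Advanced Life Support measures to control symptoms".
- Reporting: "AEs and SAEs will be reported to the IRB within 5 days of the event".

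The Safety section just before it covers emergency unblinding: "If there is an untoward event that requires the treating provider to know which medication was administered, the pharmacist will unblind the randomization". The stated consequence is that "the patient will not continue in the study". It does not say whether such an event is an AE or an SAE, or whether it is recorded or reported.

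The consent paragraph under Selection of Participants names the known risks of each drug. For ketamine these include "hallucinations, bradycardia or hypotension, arrhythmias, and respiratory depression", and for prochlorperazine "akathisia, tardive dyskinesia, NMS, and blood dyscrasias".

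**The concern.** Whether a known reaction counts as an AE depends on whether treatment worked. Whether any reaction counts as serious depends on one kind of treatment, not on what happened to the patient. A reaction can therefore be bad enough for the clinician to need the allocation and for the patient to leave the trial, and still meet neither definition.

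At stake is the safety comparison between the arms. The introduction says that, to the authors' knowledge, no prospective study has evaluated ketamine for benign headache in the ED, so the IRB and later readers will look to this trial for its tolerability. If treated and resolved reactions are left out of the AE count, a low count could be correct under the protocol's definitions and still understate what happened.

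**Working it through.** The point concerns definitions, and the plan gives no figure to reproduce. The check applies the definitions to each kind of event and then asks what else would capture the events left out.

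**Step 1: apply the definitions.** From Reportable Events:

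- AE = (unanticipated and needs intervention) or (anticipated and does not respond to intervention)
- SAE = needs Advanced Life Support (ALS)
- Reportable = AE or SAE

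Four yes/no attributes give 2 × 2 × 2 × 2 = 16 combinations. Without intervention, response and ALS do not arise, so 8 + 2 = 10 remain.

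| Anticipated | Intervention | Responds | ALS | AE | SAE | Reportable |
|---|---|---|---|---|---|---|
| yes | yes | yes | yes | no | yes | yes |
| yes | yes | yes | no | no | no | **no** |
| yes | yes | no | yes | yes | yes | yes |
| yes | yes | no | no | yes | no | yes |
| yes | no | n/a | no | no | no | **no** |
| no | yes | yes | yes | yes | yes | yes |
| no | yes | yes | no | yes | no | yes |
| no | yes | no | yes | yes | yes | yes |
| no | yes | no | no | yes | no | yes |
| no | no | n/a | no | no | no | **no** |

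Seven are reportable and three are not. Two of the three need no intervention. The second row is the one that matters: an anticipated effect that needs treatment, responds and needs no ALS.

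**Step 2: read the sentence on anticipated effects.** It can be read in two ways.

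- Reading A: anticipated means listed on the insert, and listed effects handled as routine are exempt. An urgent listed reaction is then outside the exemption but still anticipated. If it responds and needs no ALS, it is neither AE nor SAE, and no rule covers it.
- Reading B: anticipated means listed and also handled as routine. An urgent listed reaction is then unanticipated. If it needs intervention, it is an AE reportable within 5 days.

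The AE sentence itself allows for anticipated effects that need intervention, so needing treatment does not by itself make an effect unanticipated.

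**Step 3: set the unblinding rule beside this.** Its trigger is an untoward event for which the provider must know the drug. It is not tied to either definition, and unblinding triggers no report. Under Reading A, an event in the second row can break the blind and end participation with no report.

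**Step 4: what is captured anyway.** Under Methods of Measurement, nausea, vomiting, anxiety, akathisia, heart rate and blood pressure are assessed at 15, 30, 45 and 60 minutes, whatever the AE status. Admission is a secondary outcome, but no item for its cause is described. Arrhythmia (beyond the heart rate readings), respiratory depression and hallucinations have no scheduled item. The 24-48 hour call asks about satisfaction and current headache only. A patient withdrawn after unblinding may also miss the remaining scheduled assessments.

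**Step 5: size, by assumption.** The documents give no rate for such reactions. Suppose 2 of 35 ketamine patients have an urgent, treated, responding reaction without ALS, and both are unblinded: 2/35 = 5.7%. Under Reading A there are 0 AEs and 0 SAEs. Under Reading B there are 2 AEs and 0 SAEs.

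Over a range of assumed rates p, the expected number in an arm of 35 is 35p and the chance of at least one is 1 − (1 − p)^35:

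| p | Expected | Chance of at least one |
|---|---|---|
| 2% | 0.7 | 50.7% |
| 5% | 1.75 | 83.4% |
| 10% | 3.5 | 97.5% |

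**The case against.** The strongest reply is that Reading B is natural. The sentence on anticipated effects refers to urgency, so the definitions do take some account of severity, and an urgent reaction that forces unblinding would be an AE. This stands as a possible reading. It does not settle the matter, because the wording equally allows Reading A and a site would have to choose.

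A second reply is that anticipated is defined by the package insert, not by the consent paragraph, and the inserts are not in the documents. This also stands. The consent list makes it plausible that arrhythmia or respiratory depression would be classed as anticipated, but does not prove it.

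A third reply is that the section governs notification to the IRB and does not say that other events go unrecorded or unpublished. That is correct, and the chart would hold some of the information. But the plan describes no form item or outcome through which the missing reactions would reach the comparison by arm.

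A reader might also infer three stronger claims that the documents do not support.

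- That every event not needing ALS escapes reporting. The ALS condition limits only the SAE class. Unanticipated effects needing intervention, and anticipated ones that do not respond, are AEs without it.
- That the safety count must come out near zero. Seven of the ten combinations are reportable, and the scheduled measures would show hypotension, bradycardia, vomiting and akathisia if present at the assessment times.
- That the Safety and Reportable Events sections contradict each other. Both can be followed at once. What is missing is a statement linking them.

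**Conclusion.** The point holds as a gap in the definitions, and the wording should be changed. On the plain reading, a listed side effect that is treated, responds and does not need Advanced Life Support is neither an AE nor an SAE. For urgent events of this kind the text is ambiguous. Nothing makes an event that breaks the blind reportable.

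The consequence is possible under-counting of treated reactions, mainly of types with no scheduled collection. Its size cannot be derived from the documents. In the assumed example it is between 0 and 2 uncounted events among 35 patients, depending on the reading. The conclusion assumes that the reactions in question appear on the package inserts. It does not affect the sample size calculation.

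**What to change.** Make four changes to the wording and the data form.

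1. Add one line to the data form to record every untoward event that needs intervention or leads to unblinding, whether or not it was anticipated, and tabulate these by arm.
2. State that any event leading to emergency unblinding is recorded and reported as an AE.
3. Base the SAE class on the outcome of the event, for example death, threat to life, or admission because of the event, and not only on use of Advanced Life Support. These examples are suggestions and do not come from the documents.
4. Reword the sentence on anticipated effects so that it has one meaning for urgent events, and reconcile the Safety and Reportable Events sections.

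The cost is protocol wording, one form line and perhaps a few more IRB reports in a trial of 70 patients. Treatment and the efficacy analysis do not change.
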